5.0 STUDY OBJECTIVES

The primary objective of this clinical investigation is:

To compare the relative clinical utility of BUP/NX to clonidine in a short-term (13-day) opiate detoxification initiated in an inpatient setting. It is hypothesized that BUP/NX detoxification, compared to clonidine, will be associated with a better treatment response. A treatment responder is anyone who completes the 13-day detoxification and whose last urine specimen collected on day 13 or 14 is negative for opiates.

Other primary objectives are:

To determine the effect of treatment on:

- 1) abstinence from opiate and other drugs of abuse throughout the detoxification period and during longer term follow-up,
- 2) withdrawal symptoms,
- 3) treatment retention,
- 4) safety,
- 5) patient satisfaction with the treatment, and
- 6) extent of ancillary medications dispensed.

Analysis of the data designed to assess the other primary objectives in combination with the primary objective will provide a comprehensive overview of the relative clinical utility (effectiveness) of the two treatment regimens.

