11.5.2 Clonidine

Patients receiving oral clonidine will be instructed to swallow all pills and/or to leave their clonidine patch in place until replaced by medical personnel or until medical personnel directs the patient to change their dosage. The clonidine detoxification protocol was designed to reflect what is being used in clinical practice at a number of the participating CTP sites. Patients will be seen daily, on days of outpatient clinic operations.

In outpatient CTP sites, clonidine detoxification should be started early in the week (Tuesday or Wednesday [see section 11.4]) to insure a steady state level before the weekend with less medical staff. Medical personnel familiar with clonidine need to be available during clonidine treatment for daily patient monitoring, dose adjustment, and prescribing ancillary medication. Medical personnel should be familiar with monitoring vital signs for orthostatic changes and responding to any changes noted. Insure consistency in monitoring by using the same B.P. device at each visit.

Clonidine Dosing Procedure:

Day 1:

Encourage patients to drink lots of fluid. Dehydration exaggerates the hypotensive effects of clonidine. Before administering the test dose of clonidine, ask patients for any history of hypertension or hypotension, fainting or dizziness on rising. Take vital signs noting especially the systolic B.P. Check the EKG to insure the PR interval is not prolonged i.e. > .20 seconds. If the patient has systolic B.P. < 100 mm Hg or heart rate < 56 bpm, do not proceed with the clonidine test dose. Reassess patient if clinically warranted or discontinue the patient from the study.

Be cautious with patients with a history of hypertension or hypotension, fainting or dizziness on rising. Instruct all patients to get up slowly while taking clonidine (e.g. "sit up, swing your feet, and count to 10 before getting up").

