11.8 Clinical Assessments During Study Interventions

Adverse events and the use of any concomitant medications occurring since the last dosing will be recorded. VAS, COWS, and ARSW assessments will be performed daily during detoxification. Urine specimens for drug testing will be collected on days 3 or 4, 7 or 8, 10 or 11, and 13 or 14. If the subject terminates early, collect all assessments scheduled for days 13 or 14 at the final study visit.

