12.18 Urine Drug Screen

Urine samples are always to be collected before dispensing medications. All urine specimens will be monitored by staff using drug test cups with temperature controlled monitoring. These cups will be provided by the Northwest Toxicology via the Center for Toxicology in Utah, which will serve as the central laboratory contractor for this protocol. Specimens will be shipped to the Center for Toxicology in Utah for subsequent analysis for opioids, methadone, benzoylecognine (a cocaine metabolite), amphetamines, cannabinoids, and benzodiazepines in accordance with the detailed procedures described in the protocol Operations Manual. Urine will be collected at baseline, on days 3 or 4, 7 or 8, 10 or 11, and 13 or 14 during detoxification, and at each follow-up visit. An additional portion will be placed in the backup cup provided by the contractor for storage at the site until the contractor completes analyses and records the data.

Additionally, an FDA-approved one-step test, the Accutest Multi-Drug Screen (for immunoassay of 9 drugs of abuse and TCAs; JANT Pharmacal Corporation) will be used during the baseline/screening phase and at the final study visit for immediate feedback of results for urine drug screening. Following collection of the urine sample into the cup provided by the central contractor, staff will dip this multi-drug screen cassette into that cup and wait for the results. Results are obtained in 3-8 minutes. Once the results

from the Accutest Screen have been recorded on the CRF, the Accutest Screen will be shipped to the central contractor, along with the other specimen of urine collected, for confirmatory analyses by the central contractor.

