12.19 Study Compliance

The amount of BUP/NX or clonidine administered daily to each patient will be recorded on a dosage log. For BUP/NX tablets or clonidine given to patients to self-administer on weekends, the daily report of medications used will be provided by the patient and recorded by study staff onto the medication logs at the next scheduled clinic visit.

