14.0 ANALYTICAL PLAN

14.1 Statistical Hypotheses

Primary Efficacy Endpoint: It is hypothesized that BUP/NX detoxification, compared to clonidine, will be associated with a better treatment response. A treatment responder is defined as anyone who completes the 13-day detoxification and whose last urine specimen is negative for opiates. By combining treatment retention with opiate abstinence, a composite number is derived that is indicative of both the patients' tolerance to the treatment and the desired outcome of abstinence at the completion of a short-term detoxification procedure. Note that there is no issue concerning the handling of missing data when utilizing this definition of "responder." Patients who fail to either come in or provide a urine sample are, by definition, non-responders.

Other Primary Efficacy Endpoint: Other primary efficacy endpoints were selected to examine the effect of treatment on 1) opiate and other drugs of abuse abstinence throughout the detoxification period and during longer term follow-up, 2) withdrawal symptoms, 3) treatment retention, 4) safety, 5) patient satisfaction with the treatment and 6) extent of ancillary medications dispensed to provide a comprehensive overview of the clinical efficacy and safety of the two treatment regimens.

Hypotheses for the other primary outcome measures include that BUP/NX detoxification, compared to clonidine, will:

- 1. Increase the number and consecutive duration of opiate and all drug-free urine specimens during detoxification and follow-up.
- 2. Increase the number of days retained in treatment.
- 3. Decrease the amount of ancillary medications needed to treat withdrawal symptoms.
- 4. Lessen the severity of withdrawal symptoms as assessed by COWS, ARSW, and VAS.
- 5. Lessen the severity of dependence or abuse as assessed by ASI Lite.

6. Improve the quality of life as assessed by the SF-36 questionnaire and satisfaction with treatment (CSQ).

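### The primary responder is defined with a day limit in 5.0 and without one in 14.1; the day 13 or 14 limit can exclude compliant Monday starters discharged before day 13, and methadone is outside the rule

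*Protocol*

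**What the plan says.** Section 5.0 of the protocol makes response depend on completing the 13-day detoxification and on a patient "whose last urine specimen collected on day 13 or 14 is negative for opiates". Section 14.1 defines the same endpoint as anyone who "completes the 13-day detoxification and whose last urine specimen is negative for opiates", with no day attached to the specimen. It adds that "Patients who fail to either come in or provide a urine sample are, by definition, non-responders", and says that missing data therefore raise no issue for this endpoint.

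Section 11.8 fixes the sampling days: "Urine specimens for drug testing will be collected on days 3 or 4, 7 or 8, 10 or 11, and 13 or 14". Section 12.18 and Table 1 give the same days, and none of the three allows another day for the last specimen.

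On setting, section 8.0 says that inpatient stay typically lasts 5 to 13 days, with the remainder as an outpatient where necessary. The clonidine section, 11.5.2, says: "Patients will be seen daily, on days of outpatient clinic operations". Section 12.19 foresees weekend self-dosing in both arms ("For BUP/NX tablets or clonidine given to patients to self-administer on weekends"), with the patient's report logged at the next clinic visit. The one site described in Appendix I runs its outpatient program five days a week and its residential program seven.

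On analytes, section 12.18 sends specimens for "subsequent analysis for opioids, methadone, benzoylecognine (a cocaine metabolite" and other drugs. Section 14.2.2 also names methadone beside opiates, not within them, in the all-drug outcomes.

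**The concern.** This endpoint sets the sample size and is the one named first for the between-arm test. Three features leave it poorly fixed.

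- A completer whose latest specimen dates from day 10 or 11 is a non-responder under 5.0 but may be a responder under a literal reading of 14.1. Two analysts could count the same patient differently.
- The 5.0 window is two consecutive days, which can both fall on a weekend. A patient who took all the treatment and stayed abstinent could then fail because the clinic was shut.
- The rule tests opiates only. A completer whose specimen is opiate-negative and methadone-positive is a success on paper. Yet section 4.0 names opioid abstinence as an objective of such a program, and section 11.3 gives a methadone-positive urine as an example of something that prevents randomization.

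At stake are the response rate in each arm and, if the calendar loss is unequal, the comparison itself.

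**Working it through.** The plan gives no figure on this point to reproduce. The check is a weekday count followed by a comparison of sections.

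**Step 1: weekdays.** With the first dose on day 1, day k falls (k − 1) mod 7 weekdays after the start day. For day 13 the shift is 12 mod 7 = 5; for day 14 it is 13 mod 7 = 6; for day 15 it is 14 mod 7 = 0.

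| Start | Day 13 | Day 14 | Day 15 |
|---|---|---|---|
| Mon | Sat | Sun | Mon |
| Tue | Sun | Mon | Tue |
| Wed | Mon | Tue | Wed |
| Thu | Tue | Wed | Thu |
| Fri | Wed | Thu | Fri |
| Sat | Thu | Fri | Sat |
| Sun | Fri | Sat | Sun |

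Only a Monday start puts both permitted days on a weekend. Adding day 15 gives every start day at least one weekday.

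**Step 2: who is exposed.** Three conditions must hold together: a Monday start, discharge before day 13, and no weekend collection at that clinic. The share lost in an arm is

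m = P(Monday start) × P(discharged before day 13, given Monday start) × P(no weekend collection, given both).

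If intake were even, the first factor would be 1/7 over seven days or 1/5 over weekdays. That is an assumption. The documents give neither of the other two factors, so m cannot be computed.

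**Step 3: direction.** Let p_B and p_C be the response rates that would be seen if every completer could be sampled, and d = p_B − p_C. Assume that the loss is unrelated to response.

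- Same m in both arms: the difference becomes (1 − m)p_B − (1 − m)p_C = (1 − m)d, that is, d reduced by m·d.
- Loss in BUP/NX only: the difference becomes (1 − m)p_B − p_C = d − m·p_B.

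Since p_B is at least as large as d, the second case costs more and works against BUP/NX. It is possible because 11.5.2 advises a Tuesday or Wednesday start for clonidine at outpatient sites, and Step 1 shows that both keep a weekday in the window. Section 11.5.1 has no such advice for BUP/NX. The advice cites section 11.4, which contains no weekday rule.

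**Step 4: the two definitions applied to one patient.** Take an exposed Monday starter who completes. The previous specimen was due on day 10 (Wednesday) or day 11 (Thursday). Suppose it was opiate-negative.

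- Section 5.0: no specimen on day 13 or 14, so a non-responder.
- Section 14.1, definition: the last specimen is "whose last urine specimen is negative for opiates"-compliant, so a responder.
- Section 14.1, missing-sample sentence: no final sample was given, so arguably a non-responder.

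Section 14.1 does not settle the case even on its own.

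**Step 5: methadone.** Sections 12.18 and 14.2.2 both treat methadone as a separate result. Sections 5.0 and 14.1 use the opiate result alone. A completer positive only for methadone therefore meets both definitions. The documents do not say how often this would occur.

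**The case against.** A reader might infer that outpatients who start on a Monday cannot meet the rule at all. The documents do not support that. No section says that outpatient collection stops at weekends at every one of the roughly six sites: 11.5.2 speaks of fewer medical staff, not none. Section 7.0 says that discharged patients follow the inpatient procedures, and patients still in hospital on day 13 are unaffected. Nor do the documents say how many patients finish as outpatients. All of this stands, and it limits the point to the three joint conditions above.

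A reader might also attach a loss of power by shrinking the 20% and 30% response rates of section 14.6. That is not supported. Those are rates of an endpoint that already counts an absent urine as failure, so the reduction may count the same loss twice, and the shares would be assumed.

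On the wording conflict, 14.1 can be read as shorthand for 5.0, because every schedule places the last detoxification specimen on day 13 or 14. That is a fair reading, but it restores the calendar problem. The looser reading eases the calendar problem but contradicts 5.0. One of the two difficulties remains either way.

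On methadone, such a patient is classified as the rule is written, and the all-drug outcomes in 14.2.2 do capture methadone. Adding the same number of percentage points to each arm would leave the difference unchanged. So this is a gap between endpoint and aim, not a demonstrated bias.

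**Conclusion.** The point holds in limited form. The disagreement between 5.0 and 14.1 and the omission of methadone follow from the text without any assumption. The calendar failure is certain for a Monday starter who has been discharged before day 13 and whose clinic does not collect at weekends. The protocol foresees the ingredients of that case (early discharge, weekend self-dosing, a five-day outpatient program at the described site) and provides no other sampling day.

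Its size cannot be derived. The documents do not give the shares of Monday starts, early discharge, weekend closure or methadone-only positives. Unequal loss between arms is a possibility rather than a finding: it depends on the clonidine start-day advice being followed, and that advice is addressed to outpatient sites in a trial that starts patients as inpatients. A reader might go on to infer that responders are misclassified in both directions to a known extent, but the documents show only that each route exists.

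**What to change.** - Use one definition in 5.0 and 14.1: the patient completes the 13 days, and the urine from the first clinic day on or after day 13, up to day 15, is opiate-negative by the central laboratory. A patient with no specimen in that window is a non-responder.
- Extend the final urine window in Table 1, 11.8 and 12.18 to days 13 to 15.
- Require the same specimen to be methadone-negative. If the opiate-only rule is kept as primary, report the responder analysis with the methadone criterion beside it.
- Reconcile the start-day advice in 11.5.2 with section 11.4, which it cites and which has no such rule.

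The cost is an amendment to the endpoint wording and to one visit window. No new assay is needed. The downsides are a sample up to one day later than now for some patients, hence slightly more variation in time since the last dose, and slightly lower response rates if methadone is added.

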6.0 STUDY SPONSOR

[name] is the study sponsor. This study will be conducted under IND # 34,563 held by [name].

7.0 STUDY SITES

The study will be conducted at approximately 6 CTP sites. Patients participating in this study will be housed initially in one of the inpatient settings described in Appendix I and follow the usual inpatient routine. Patients who are discharged prior to completing the 13-day detoxification protocol will continue on their assigned detoxification regimen using the same procedures as if they were still inpatients. Discharge to complete the study by outpatient detoxification could occur because of patient's choice, insurance coverage, or CTP's standard detoxification procedures.

8.0 STUDY DESIGN

A randomized, open-label, parallel groups study design will be used. After screening and baseline assessments, patients will be stratified for gender and randomly assigned in a 2:1 ratio to either a BUP/NX or clonidine 13-day detoxification. Patients will initiate detoxification in the inpatient setting and, as necessary, will continue detoxification as outpatients for the full 13 days. This typically ranges from 5 to 13 days of inpatient detoxification. After the 13 day detoxification, patients will be assessed for outcome measures including relapse and withdrawal symptoms at follow-up visits occurring 1, 3, and 6 months after starting detoxification. Counseling procedures in existence at each CTP will be used throughout the study. Self-help detoxification handbooks will be distributed to all study participants.

9.0 PATIENT SELECTION

A total of 360 male and female patients diagnosed with opiate dependence will be enrolled in the study (240 in the BUP/NX group and 120 in the clonidine group). Entry into this study is open to both men and women and to all racial and ethnic groups. Each of the participating CTP sites will enroll approximately 60 patients. Patients will be recruited by word of mouth, referrals from local narcotic treatment and outreach programs, outpatient and inpatient alcohol and drug abuse clinics, PCPs, local mental health centers and crisis clinics, public service announcements, newspaper advertisements and hospital emergency rooms. Recruitment advertisements will be approved by each site's Institutional Review Board (IRB).

9.1 Inclusion Criteria:

- 1. Treatment-seeking males and non-pregnant and non-lactating females, 15 years and older, who fulfill DSM-IV criteria for opiate dependence, report experiencing symptoms of opiate withdrawal, are currently physically dependent on opioids, and are need of medical assistance for opioid withdrawal.
- 2. Systolic blood pressure ≥ 100 mm Hg, and pulse ≥ 56 bpm.
- 3. Good general health or, in case of a medical/psychiatric condition needing ongoing treatment, under the care of a physician willing to continue patient's medical management and cooperate with the study physicians.
- 4. Agreeable to and capable of signing the informed consent approved by an institutional review board and, if under the age of 18 (excluding emancipated minors), assent and concurrent consent from a parent or legal guardian.
- 5. Use of one of the following acceptable methods of birth control by female patients of childbearing potential:
 - a. oral contraceptives
 - b. barrier (diaphragm or cervical cap) with spermicide or condom
 - c. intrauterine progesterone contraceptive system
 - d. levonorgestrel implant
 - e. medroxyprogesterone acetate contraceptive injection
 - f. complete abstinence from sexual intercourse

9.2 Exclusion criteria:

- 1. Medical condition that would make participation, in the opinion of the study physician, medically hazardous (e.g., acute hepatitis, unstable cardiovascular, liver or renal disease);
- 2. Clinically significant abnormalities in ECG.

- 3. Known allergy or sensitivity to buprenorphine, naloxone, or clonidine.
- 4. Receiving beta-blockers, calcium channel blockers, tricyclics, digitalis and other medications which may interact adversely with clonidine.
- 5. Acute severe psychiatric condition in need of immediate treatment, or imminent suicide risk.
- 6. Dependence on alcohol, benzodiazepines or other depressants, or stimulants, and requiring immediate medical attention.
- 7. Participation in an investigational drug study, including buprenorphine, within the past 30 days.
- 8. Methadone or LAAM maintenance or detoxification within 30 days of enrollment.
- 9. Pending legal action that could prohibit or interfere with participation.
- 10. Unable to remain in area for duration of active phase of treatment.
- 11. Females that are pregnant, lactating, or planning to become pregnant.

10.0 INVESTIGATIONAL AGENTS

BUP/NX-combination:

Buprenorphine 2 mg and naloxone 0.5 mg or buprenorphine 8 mg and naloxone 2 mg sublingual tablets are manufactured by Reckitt and Colman Products (Hull, UK) and will be supplied through the National Institute on Drug Abuse and Research Triangle Institute.

Clonidine:

Clonidine (CATAPRES[®]- clonidine hydrochloride USP) is commercially available and is manufactured by Boehringer Ingelheim Pharmaceuticals, Inc., Ridgefield, CT. The clonidine to be used for this study is a 0.1 mg tablet for oral dosing and a transdermal therapeutic system (CATAPRES-TTS[®] - 1, 0.1 mg per day, for one week).

Ancillary Medications:

Ancillary medications used to treat opiate withdrawal side effects are commercially available and include:

Over the counter medications:

acetaminophen 650 mg

ibuprofen 200 mg loperimide 2 mg diphenhydramine 25 mg

Prescription medications:

oxazepam, tablets or capsules 15 mg and 30 mg
lorazepam, tablets 0.5 mg, 1 mg, and 2 mg
phenobarbital tablets, 15, 16 and 30 mg, capsules 16 mg
hydroxyzine hydrochloride tablets, 50 mg
methocarbamol tablets, 500 mg and 750 mg
trimethobenzamide capsules, 250 mg or 100/200 mg suppositories

Donnatal tablets or capsules – atropine sulfate 0.0194 mg, scoplamine hydrobromide
0.0065 mg, hyosyamine hydrobromide or sulfate 0.1037 mg, and phenobarbital 16
mg
zolpidem tartrate tablet, 5 and 10 mg
trazadone hydrochloride tablets 50 mg, 100 mg, 150 mg and 300 mg
doxepin hydrochloride tablets, 50 mg

10.1 Dispensing Investigational Agents

Investigational agents will be dispensed daily according to the appropriate study arm while patients are in the inpatient setting. If patients are released for outpatient detoxification, investigational agents will continue to be dispensed in accordance with the inpatient procedures. Investigational agents will be prescribed, dispensed or administered (furnished) by an individual legally qualified to do so in accordance with state regulations. Patients receiving BUP/NX will be instructed to hold the tablet(s) under their tongue until dissolved. Dissolution of tablets will be monitored as clinically warranted by a nurse, physician or pharmacist at each CTP. Patients receiving oral clonidine will be instructed to swallow all pills and/or to leave their clonidine patch in place until replaced by the nurse, physician, or pharmacist at the study site.

For both in- and outpatient settings, it is recommended that patients be observed for at least several hours on the first day of treatment following the administration of bup/nx or clonidine until vital signs are stable.

Additionally, as clinically indicated, outpatients should not be allowed to drive home by themselves on the first (and sometimes second) day of bup/nx or clonidine treatment.

